1. Ketorolac Research Form: this form documents age, gender, pain location, inclusion criteria, exclusion criteria, objective adverse effects, and subjective adverse effects. No PHI or PII will be annotated on this form.
  1. Age will be documented in years only. The actual date of birth will not be documented.
  2. Gender will be documented as "M" for male or "F" for female. Or an appropriate box will be "checked" by the potential subject indicating subject gender.
  3. Pain location will be free text, but will be qualified and isolated to an anatomical region. This will be at the discretion of the investigator. For instance, "heel pain" would be annotated as foot pain, or "calf pain" as leg pain. The anatomical regions designated for the purposes of this research are: (1.) neck pain, (2.) shoulder pain, (3.) arm pain, (4.) elbow pain, (5.) forearm pain, (6.) wrist pain, (7.) hand pain, (8.) hip pain, (9.) thigh pain, (10.) knee pain, (11.) leg pain, (12.) ankle pain, (13.) foot pain or (14.) back pain.
  4. See inclusion and exclusion section in this document for a detailed description of both.
  5. Adverse events which occur due to administration of intramuscular ketorolac will be documented as objective and subjective adverse effects. [Note, "adverse events" is a phrase used to describe adverse events, reactions, and effects to intramuscular ketorolac.] Subjects will be provided a list of known adverse events occurring in greater than 1% of patients during the U.S. Food and Drug Administration (FDA) trials, according to the medical website UpToDate.com. The list of adverse events will be included on the Ketorolac Research Form. Subjects will be advised to circle any of the adverse events that they are experiencing. Each circled adverse event will count as 1 in a binary numbering system (1 indicating an adverse event and 0 indicating no adverse event) for purposes of analysis. Subjects may have more than one adverse event and each event will count as 1 point. The definitions of objective and subjective adverse event are provided below.

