The subject's EHR will not be accessed for any reason for the purposes of this research. All PHI or PII will be gathered on paper and will be provided voluntarily by the study subject. This information will be de-identified after consent is obtained and only the study subject randomized number will be used for identification.

All paper documents will be held in a locked locker in the WBAMC ED for the duration of the data collection period, analysis period, and as the manuscript is produced. Upon completion of the manuscript, the documents will be securely transferred to the WBAMC room 10015 and secured in a locked cabinet for a period of up two years. Upon completion of the three year, post-study period, the documents will be destroyed in accordance with WBAMC sensitive document disposal policies.

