### **11.0 Statistical/Data Analysis Plan**

#### **11.1 Statistical Considerations:**

List the statistical methods to be used to address the primary and secondary objectives, specific aims, and/or research hypotheses. Explain how missing data and outliers will be handled in the analysis. The analysis plan should be consistent with the study objectives. Include any sub-group analyses (e.g., gender or age group). Specify statistical methods and variables for each analysis. Describe how confounding variables will be controlled in the data analysis

The primary outcome will be the difference in VAS from baseline to 30 minutes and from baseline to 60 minutes. Our research hypothesis is that the measured pain relief using 15mg of intramuscular ketorolac will be non-inferior to the measured pain relief using 60mg of intramuscular ketorolac. Whereas in a clinical study where the research hypothesis is that one treatment, say drug A, is demonstrated to have a better (improved pain relief) outcome than the second treatment, say drug B, we are hypothesizing that smaller dose drug is not inferior in terms of pain relief than the higher drug dose. We fully suspect that the higher drug dose will have a better average outcome, but the question of interest is, is the outcome for the lower dose drug non-inferior to that of the higher drug dose. The analysis used in this study is a non-inferiority test. This hypothesis can be tested using a variety of methods that involve the construction of one-sided confidence interval or one-sided, two-sample equal-variance t-test with alpha of 0.05. In both methods, the power and sample size can be computed.

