**11.5 Please provide a justification for your sample size**

In this study, we assume that we are comparing the mean VAS between the 2 Groups, and the margin of non-inferiority is -13 mm. The actual difference between the means is assumed to be 0 and the standard deviation is assumed to be 27 for the 2 Groups (estimated from the Motov manuscript). Group sample sizes of 55 and 55 achieve 80% power to detect non-inferiority using a one-sided, two-sample equal-variance t-test with alpha of 0.05. The sample size per arm was increased from 55 to 61 to account for an anticipated 10% dropout or withdrawal of subjects (5.5 subjects was rounded to 6 subjects).

**11.6 Data Analysis Plan: Complete description: Background, Objectives, Design, Step by Step how the project is going to be done, Data analysis plan:**

To test for non-inferiority of dose 15mg to dose 60 mg using the VAS pain score, the analysis to be used is called an interval test. The hypothesis will be tested using the construction of one-sided confidence intervals or one-sided, two-sample equal-variance t-test with alpha of 0.05. To test that the lower dose has less adverse effects, we will use the one-sided z-test for testing two independent proportions. All tests will be conducted at the 0.05 level of significance.

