Cover Page

Title: Comparison of Intramuscular Ketorolac at Two Single-Dose Regimens for Treatment of Acute Musculoskeletal Pain in a Military Emergency Department: A Randomized Controlled Non-Inferiority Trial

NCT: Not received yet

Date: 2/5/2021

Statistical Analysis Plan

Data analysis will be performed using the statistical software SPSS (IBM SPSS Statistics for Windows, Version 26.0. Armonk, NY: IBM Corp.). The primary outcome will be tested using an independent samples *t*-test. To assess for any differences in VAS scores based on demographic data, independent *t*-tests will be utilized. To assess for normality of distributions in the sample's continuous demographic and clinical characteristics, z-scores will be formed by dividing skewness by the standard error of skewness. This is performed to ensure that parametric measures can be used for the two groups. A Fisher's exact test will be used to assess the lower dose for a difference in adverse effects. During analysis, it was determined that the pain reduction variables could be compared by age and body weight using Pearson correlations. Additionally, the pain reduction variables will be compared by gender, duration of pain (\leq 24 hours vs. $>$ 24 hours), and location of pain (back/neck vs. other locations and small vs. large joints) using independent *t*-tests.

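### The SAP lists twelve secondary tests of pain reduction, four of them chosen during analysis, with no exploratory label, dose term or multiplicity control

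*SAP*

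**What the plan says.** **SAP.** The plan is a single paragraph. It names an independent-samples t-test for the primary outcome, t-tests of VAS by demographic data, a normality check and Fisher's exact test for adverse effects. It then says: "During analysis, it was determined that the pain reduction variables could be compared by age and body weight using Pearson correlations". The next sentence reads "Additionally, the pain reduction variables will be compared by gender, duration of pain", dichotomised at 24 hours, and adds "location of pain (back/neck vs. other locations and small vs. large joints", all by independent t-tests. Nothing marks these comparisons as post hoc or exploratory. No dose term, stratum or interaction is given, and no multiplicity adjustment.

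**Protocol, analysis.**
- Section 11.1 defines two pain-change variables: "The primary outcome will be the difference in VAS from baseline to 30 minutes and from baseline to 60 minutes". Its template asks for subgroup analyses with methods and variables; the answer names none.
- Section 11.5 gives the −13 mm margin and a one-sided test. Section 11.6 adds: "All tests will be conducted at the 0.05 level of significance".
- Section 10.2, under descriptive statistics, foresees age, gender, location and duration of pain as descriptive data, and leaves significance testing to the statistician.

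**Protocol, body weight.**
- It appears only in 12.6, as the exclusion below 50 kg.
- Section 10.1 summarises the research form thus: "this form documents age, gender, pain location, inclusion criteria, exclusion criteria, objective adverse effects, and subjective adverse effects". It limits protected health information to chief complaint and vital signs.
- Section 13.3 opens the vital-signs screen for heart rate, temperature and blood pressure.
- Section 10.14 says of the record system: "EHR will not be accessed for any reason for the purposes of this research".

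**The concern.** Under protocol 10.2 the VAS forms are measured only after collection is complete for the whole study. A decision taken during analysis about what to compare with pain reduction was therefore probably taken with outcome data available. Such comparisons can be worth reporting, but a nominal p-value from them does not carry the weight of a planned test. Here they follow the primary test in the same paragraph, under a protocol that applies 0.05 to everything. The report could then present one or two chance associations as trial findings.

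Two further matters affect what the tests could mean.
- As described, they compare pain relief between kinds of patient, not between doses. A difference between back pain and other pain says nothing about whether 15 mg does relatively worse in either group.
- These factors are not randomised. A raw change score also mixes any relation with pain relief with differences in starting pain.

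Finally, a plan partly settled during analysis gives the primary t-test without margin or direction, whereas the protocol's rule has both.

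**Working it through.** **1. The plan's own figure.** The documents give no test count or family-wise error for these comparisons. The nearest stated figure is 55 per arm (11.5: margin 13 mm, SD 27 mm, true difference 0, one-sided 0.05, 80% power).

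Normal approximation: n = 2 × 27² × (1.645 + 0.842)² / 13² ≈ 53.4, so 54 per arm. The exact noncentral t gives 79.98% power at 54 and 80.6% at 55. The stated 55 reproduces, and the secondary comparisons do not affect it.

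**2. Test count.** Taking the SAP's pain reduction variables to be the two in 11.1 (30 and 60 minutes):

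| Group | Factors | Tests |
|---|---|---|
| Worded as decided during analysis | age, body weight | 2 × 2 = 4 |
| Added in the next sentence | gender, duration, back/neck split, joint-size split | 4 × 2 = 8 |
| Total | 6 | 12 |

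The SAP's earlier demographic t-tests are not counted. Protocol 10.2 describes demographics as age and gender, so counting them could count the same tests twice.

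**3. Chance findings if no factor is related to pain reduction.** For k independent tests at 0.05, P(at least one) = 1 − 0.95^k.
- k = 4: 1 − 0.95⁴ = 18.5%
- k = 12: 1 − 0.95¹² = 46.0%
- Expected false positives over 12 tests: 12 × 0.05 = 0.60
- Bonferroni level for 12 tests: 0.05/12 = 0.0042

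**4. Allowing for correlation.** The two changes share a baseline and the same patients, so independence overstates the risk. Their correlation is not in the documents. It was assumed, and the 12 tests were simulated (110 subjects, 8,000 runs, mutually independent factors).

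| Assumed 30/60-minute correlation | P(at least one false positive) |
|---|---|
| 0 | 46% |
| 0.5 | 43% |
| 0.7 | 41% |
| 0.9 | 36% |
| 1 (6 effective tests, 1 − 0.95⁶) | 26.5% |

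The last row is the floor for dependence between time points. Overlap between factors, such as the two location splits, would lower all rows somewhat; the documents give no basis for saying by how much.

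**5. Does omitting dose invalidate the tests?** With a true dose difference of 13 mm left out of the model and factors independent of dose, the simulated error rate was 5.0% per test. Pooling over dose does not inflate false positives. The loss is one of interpretation.

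**6. What an interaction could show.** Assume SD 27 mm, 110 subjects, a factor splitting each arm in half (27.5 per cell) and no gain from baseline adjustment. The SE of the difference between two subgroup dose effects is 27 × √(4/27.5) = 10.3 mm. The 95% half-width is about 1.98 × 10.3 = 20 mm, wider than the 13 mm margin.

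**The case against.** The strongest reply is that much of this was foreseen and the rest disclosed. Protocol 10.2 names age, gender, location and duration and allows the statistician to test them. The SAP itself plans demographic t-tests before the sentence at issue, and that sentence says openly when the age and weight comparisons were chosen. The protocol's objectives (9.3) pose no subgroup question, so the tests need not answer one. Most of this stands, and it limits the point in several ways.

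- A reader might infer that all twelve tests were chosen after seeing data. The timing phrase covers only age and weight. The other eight are in the future tense, and calling them post hoc would be a reading. Because their cut and groupings are absent from the protocol, exploratory is the right label.
- A reader might infer concealment. The SAP's wording does not support that; what is missing is a label.
- A reader might infer that body weight could not legitimately have been collected. The form itself is not in the documents. The 10.1 summary also omits pain duration, which 10.2 places on that form, so the summary is not a complete list. Weight must be checked against the 50 kg threshold, and 10.14 allows subjects to supply information on paper. All that can be said is that no source for a weight value is listed.
- Pooling over dose is inferred from silence, and step 5 shows that it does not itself create false positives.

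The reply does not remove the need for a label. Section 10.2 treats these data as descriptive, does not set out tests of pain reduction by each factor, and does not mention weight. No reading of it supplies the 24-hour cut or the joint-size split.

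**Conclusion.** The point holds and is worth acting on, as a matter of labelling and method in secondary analyses. Four comparisons were, on the SAP's own words, decided during analysis. Eight more rest on a protocol that foresaw their variables only descriptively, and six of those (duration and the two location splits) use groupings found nowhere in it.

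The chance of at least one false positive across the twelve is 46% if they are independent. It is about 36–43% at assumed 30/60-minute correlations of 0.5–0.9, and 26.5% if the two time points coincide. These figures assume that no factor is related to pain reduction, that the six factors are mutually independent, and that there are two pain-change variables.

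A reader might go further and infer that the primary result or sample size is compromised. The documents do not support that. Nor does the SAP say that it overrides the protocol's primary rule. But since its t-test has neither margin nor direction, the governing rule should be stated.

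**What to change.** Revise the SAP paragraph as follows.

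1. Label the age and body-weight comparisons post hoc, and those by gender, duration and location exploratory. Say when the 24-hour cut and the location groupings were chosen, and define small and large joints.
2. Report estimates with 95% confidence intervals and make no significance claims for any of the twelve.
3. Analyse follow-up VAS at each time on dose, baseline VAS and the factor. Add a dose-by-factor term only if subgroup dose effects are to be described, and then show the dose difference with its interval in each subgroup.
4. State where body weight was recorded, or drop that analysis. Adding fields to the form after collection cannot supply the value.
5. State that the one-sided non-inferiority test in protocol 11.5–11.6, with the −13 mm margin, governs the primary conclusion.

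The cost is a few sentences and a modest reanalysis, with no new subjects. Some nominally significant secondary findings will be lost. Interaction estimates will be imprecise at about 110 subjects: roughly ±20 mm for an even split under the protocol's SD, so they can describe but not settle whether the dose comparison differs by subgroup.

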##### Definitions

1. Acute – onset of symptoms within 30 days on the day of data collection.
2. Musculoskeletal (MSK) – a general term used to described the various forms of pain effecting the musculoskeletal system, for this study. The types of pain included in this definition are undifferentiated muscular, undifferentiated bony, undifferentiated soft tissue, neck, back (to include cervical, thoracic, lumbar, and sacral), shoulder, arm, elbow, forearm, wrist, hand, hip, thigh, knee, leg, ankle, foot and digits).
3. Potential subject – any patient presenting to the WBAMC ED meeting age inclusion criteria with an Emergency Severity Index (ESI) score of 4 or 5 and having a chief complaint of musculoskeletal (MSK) pain, as defined above.
4. Subject – any potential subject meeting aforementioned criteria for enrollment, who met all inclusion criteria, who did not meet any exclusion criteria, who provided informed consent, and signed the Healthcare Information Portability and Accountability Act (HIPAA) Authorization Form.
5. Subject Study Packet –the packet containing documents used to annotate eligibility, acceptance, and consent to participate in the study. Forms included within the packet are the Ketorolac Research Form, Informed Consent Form, HIPAA Authorization Form, and VAS forms (1-3).

Subject Study Number – The randomized number assigned to each subject in order to de-identify data for purpose of protecting Personal Identifiable Information during the reporting of the study's results.

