**Descriptive Statistics Data.**

Descriptive statistics data will be gathered to find correlation between subject demographics (age and gender) and location and duration of pain. These data will be obtained on the Ketorolac Research Form which is completed by the subject and will be included as descriptive statistics only. The data may or may not be analyzed for statistical significance, this will be at the discretion of the statistician. Furthermore, data pertaining to subjects requiring analgesia beyond the ketorolac used for this study, will also be collected for descriptive purposes only. Furthermore, data pertaining to subjects requiring analgesia beyond ketorolac, will be collected for descriptive purposes only. The data will be collected on the Ketorolac Data Collection Workbook, along with the other data.

At the completion of the entire data collection period for the entire study, VAS measurements will be obtained based on the methodology above and all data pertaining to the primary outcome (VAS scores), secondary outcome (adverse events) and descriptive statistics (from the Ketorolac Research Form) will be transcribed on to a Microsoft Excel work sheet. Any PHI or PII at this point will be de-identified and only the Subject Study Number will be used for identification. All paper documents will be secured in a manner previously described. The Excel worksheet is located on the PIs government issued common-access-card protected laptop. Access to this laptop requires both a common-access-card and a personal identification number (PIN) assigned to that specific common-access-card. The worksheet will therefore be highly secure and saved to the hard drive of the PIs laptop. The hard drive on the computer can only be accessed by the PI (as previously discussed) and network system administrators with permission. The AI for this research may also have a copy of the de-identified data, however, the data will be stored and secured in the exact same manner as the PI (common-access-card and PIN protected). All measures will be taken to protect the information of the study, however no PHI or PII will be stored on the Microsoft Excel work sheet.

**10.3 At any point in the study, will you request, use, or access health information in any form, including verbal, hard copy and electronic?**

Yes  No

**10.4 Review the definitions below and respond to the following two questions. If you are not sure of the answers, email [contact] for assistance.**

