#### 12.5 Inclusion Criteria:

Order Number	Criteria
1	
Age 18-55 years of age
 
Study subject is one of the following; DoD service member, DoD beneficiary, or Veteran Affairs beneficiary
 
ESI 4 or 5
 
Presenting to WBAMC ED for management of musculoskeletal pain (i.e., general muscular, neck, back, shoulder, arm, forearm, elbow, wrist, finger, hip, knee, thigh, leg, ankle, foot or digits)
 
Pain intensity of 20 mm or greater on a standard 100 mm visual analog scale
 
Pain duration less than 30 days
 
Attending provider concurs with intramuscular ketorolac administration for analgesia

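### The SAP splits pain duration at 24 hours without a reason, so its t-test cannot show a gradient across the remaining 29 eligible days; a continuous analysis would use more of the data if duration was recorded as a number

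*SAP*

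**What the plan says.** The SAP's single analysis paragraph treats its secondary predictors in two ways. It says that "the pain reduction variables could be compared by age and body weight using Pearson correlations". In the next sentence it says that "the pain reduction variables will be compared by gender, duration of pain" and location of pain, and the test for these is the independent t-test. The groups for duration are up to 24 hours and more than 24 hours. No reason is given for that cut-off.

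The only other duration limit in the documents is 30 days. The protocol's Definitions (section 10.1) describe acute pain as "onset of symptoms within 30 days on the day of data collection", and the inclusion criteria (section 12.5) require "Pain duration less than 30 days".

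The protocol's Descriptive Statistics Data paragraph (section 10.2) says that duration is obtained on the Ketorolac Research Form, that these data "will be included as descriptive statistics only", and that any significance testing is left to the statistician. The description of that form in section 10.1 lists age, gender, pain location, the eligibility criteria and adverse effects. It does not list duration as an entry of its own, so the unit or format of recording is not stated.

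**The concern.** Duration is by nature a continuous measure. Under this split a 25-hour pain and a 29-day pain count as the same, while a 23-hour and a 25-hour pain count as different. If pain reduction drifts with duration anywhere between day 2 and day 30, the two-group t-test cannot show it. A null result would then say little about whether response depends on duration. The SAP already has a continuous method in place for age and weight, so the different treatment of duration looks like an unforced loss. At stake is how informative one secondary comparison is, and nothing beyond that.

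**Working it through.** **The plan's own figure.** The documents give no sample size, power or expected distribution for the duration comparison. The only calculated figure is for the primary test (protocol section 11.5): margin 13 mm, true difference 0, SD 27, one-sided alpha 0.05, power 80%, 55 per arm. The normal approximation gives 2 × (1.645 + 0.842)² × 27² / 13² ≈ 53.3, so 54 per arm. The noncentral t gives 79.98% power at 54 and 80.6% at 55, so 55 reproduces. That figure does not bear on duration. It only supplies the 110 subjects used below.

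**Information kept by a split.** When the relation is linear in a predictor X, the efficiency of a two-group split relative to X itself is the squared correlation between X and the group indicator. For a normal X (here, assumed log-duration) with a share p at or below the cut, this is φ(z_p)² / [p(1 − p)].

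- p = 0.50: 0.3989² / 0.25 = 0.637, loss 36%
- p = 0.30: 0.3477² / 0.21 = 0.576, loss 42%
- p = 0.20: 0.2800² / 0.16 = 0.490, loss 51%
- p = 0.10: loss 66%
- p = 0.05: loss 78%

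The loss reaches 50% at p = 0.209. By symmetry, a loss of 36% to 50% needs about 21% to 79% of subjects at or below 24 hours.

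**Other shapes, with the effect linear in raw time.**

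- Uniform: loss = 1 − 3p(1 − p). This is 25% at p = 0.50 and 90% at p = 1/30 (durations spread evenly over 30 days).
- Exponential: loss = 1 − [ln(1 − p)]²(1 − p)/p. This is 52% at p = 0.50, 80% at p = 0.20 and 90% at p = 0.10.
- Log-normal duration with a raw-time effect is more extreme: 73% at p = 0.50 with a log-scale SD of 1, and higher with more spread.
- True step at 24 hours: no loss, because the indicator is then the right predictor.

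**Power example.** Assume a correlation r with log-duration, n = 110 and a two-sided 5% test. With the Fisher transformation, power ≈ Φ(atanh(r_eff) × √107 − 1.96), where r_eff = r × √efficiency.

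- r = 0.25, continuous: 0.2554 × 10.344 − 1.96 = 0.68, power 75%
- r = 0.25, 50/50 split: r_eff = 0.1995, power 55% (56% by simulation)
- r = 0.25, 30/70 split: power 51%
- r = 0.25, 20/80 split: r_eff = 0.175, power 45%
- r = 0.30: about 89% continuous, against about 71%, 67% and 60% for the same three splits

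The correlations are illustrative; the documents give no value.

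**The case against.** The case for leaving the split alone has real force.

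- **The size is not in the documents.** A reader might infer that a third to a half of the information is lost as a matter of fact. The documents give no distribution of duration, no share presenting within 24 hours and no shape for the relation, so that figure is conditional. This part of the objection stands in full.
- **A real relation is not necessarily missed.** A reader might infer that the split would probably overlook a true association. In the six split scenarios above (two correlations, three splits), only one has power below 50%. The supportable statement is that power falls.
- **The split has some merits.** It is easy to read, it is not driven by a few long durations and it assumes no linear trend. If fresh injury differs from anything later, it is the better model. Pearson correlation on raw, probably skewed durations would be fragile. This stands as a reason to use a log scale or ranks and to keep the split on display. It does not explain why the split should be the only analysis.
- **It does not show where non-inferiority holds.** A reader might infer that a better duration analysis would identify the patients to whom the dose result applies. That question concerns whether the dose difference varies with duration. The SAP describes a comparison of pain reduction by duration, and a correlation pooled over arms would not answer it either.
- **The analysis is minor.** The protocol calls these data descriptive. That stands and limits the weight of the point, although the SAP does now commit to a test.
- **It may be too late to change the form.** The SAP introduces the age and weight correlations as something settled during analysis, so data may already have been in hand. The remedy therefore depends on how duration was recorded.

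**Conclusion.** The point holds as a minor, optional improvement. The text itself establishes that duration is cut at 24 hours with no reason given, that age and body weight are not cut, and that the upper group covers about 29 of the 30 eligible days, so no gradient within it can be seen.

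The size is conditional. The loss is about 36% to 50% of the information if log-duration is roughly normal, the relation is linear on that scale and about 21% to 79% of subjects present within 24 hours. The uniform and exponential shapes examined give 25% to 90%, and there is no loss under a true step at 24 hours. In the worked example at r = 0.25, the cost is roughly 20 to 30 percentage points of power.

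The documents do not support carrying this further. The primary non-inferiority test, its margin, alpha and sample size are untouched.

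**What to change.** Change one sentence of the SAP. Where duration is recorded as a number, analyse it as continuous: log duration in a correlation or as a term in a regression, or a Spearman correlation if it remains skewed. Keep the 24-hour split as a descriptive row in the table.

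State in the SAP how the Ketorolac Research Form records duration. If collection is still open, enter it as a number with its unit. If only a category was captured, keep the split and say in the report that it cannot show a gradient beyond 24 hours.

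The cost is small: no extra subjects, visits or procedures, and no change to the primary analysis. The downsides are a modelling assumption about the shape of the relation and reliance on numeric recording. If data are already in hand, label the continuous analysis as added at that stage.
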